The sample size was determined using the Gottschalk study listed in the reference section which used methadone vs. sufentanil in 29 patients undergoing lumbar fusion surgery and the measures for pain level and total narcotic usage at 48 hours to determine an 'n' for the total study population, using a power of 0.80. The details of the calculations is listed in the data analysis section (7a) below and calculated with the suggestion of the statistician on the IRB. The assumptions with which the outcomes are hypothesized are the result of previously published data using similar populations. Two sample t-tests are appropriate to determine statistical significance between mean pain scores between different patients in the control and study groups for each individual time point as there will be no censoring of the study data. Ranked T-test may also be used if outliers are present, however patients with unusual post-operative courses may be excluded if their reason for prolonged hospitalization is unrelated to immediate post-operative pain

control. The large sample size plans to take into account possible outliers that may not be included in final analysis, despite their mention in study write-up to determine why their post-operative hospitalization was prolonged. Additionally, data about patients' mean time to ambulation, mean time to discharge, and mean overall narcotic usage will be measured between the control and study populations. Data analysis will be performed with the assistance of the biostatistician listed as a member of the study team, [name], from the Albert Einstein College of Medicine, Division of Biostatistics. Thus, a sample of 60 completed methadone patients will be evaluated against 60 randomized, standard narcotic regimen controls. The mean data for control patients' pain ratings, narcotic usage, time to ambulation, and time to discharge will be obtained, the statistical deviation of this data will be measured and compared to subject data in all facets.

• Take into account anticipated drop-out or loss-to-follow up rate.

We intend to screen 200 patients to have 60 in each arm ultimately included in the study. Since the intervention is a single intra-operative occurrence, that when completed patients cannot reverse, we do not anticipate any drop-out. A two week follow-up visit is a required standard of care for all post-operative patients, without patient loss to follow-up historically. The study is completed at this point.

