Two sample T-tests will be performed to evaluate continuous variables such a total morphine dose, pain level per VAS, time to first morphine dose, time to ambulation, and time to discharge. The assistance of a statistician, [name], from the Albert Einstein College of Medicine, Division of Biostatistics will be used for statistical analyses performed in this study. Wilcoxon Rank Sum Test will be used if outliers are noted in the study population, detected as more than 5 MAD from the median, and a concern presents that single patients may skew the data. Additionally, review of these patients who are outliers may also necessitate their exclusion from this work if they provide data that will significantly modify the mean of the remaining patients. This can be accounted for in the goal of 60 patients to be accrued in each arm of the study. A thorough explanation and review will performed on any such patients in any form of write up of this work.

At least one study hypothesis (or a statement that the study is hypothesis-generating or a feasibility study):

The use of single dose intraoperative methadone will decrease total narcotic usage, time to ambulation, mean pain rating at 24 and 48 hours and will decrease number of days of hospitalization compared to sufentanil (current standard of care) controls.

• A statement regarding specifically what data are to be used to test the hypothesis (or to generate the hypotheses)

We will obtain data of total narcotic usage, days until patients ambulate with physical therapy, pain ratings at 24 and 48 hours, and days to discharge, all obtained from the patient's medical record.

- o The statistical method(s) to be used to test the hypothesis with that data
 Two-sample T-test will be used with the assistance of an Albert Einstein statistician, [name], to analyze
 the above data and determine if there is statistical significance between the two groups, in addition to the
 stipulations outlined above to address outlier patients.
- A power analysis to determine the sample size (even for pilot studies)

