 We proposed to recruit 60 patients to undergo the new treatment and another 60 as controls. This gives us greater than 80% (95%) power to detect an improvement of 0.56 (0.74) within-group standard deviation at statistical significance level 0.05 as had been calculated to be 51 patients per group. Using 60 patients will ensure the usability of our data to detect differences of this effect sizes between groups. From our preliminary data, the standard deviation of time to discharge is 6.7 days, therefore, our sample size is able to detect an average reduction of 3.8 days (5.0 days) in time to discharge with 80% (95%) power.

Describe methods for interim analyses or early stopping, if applicable A data safety monitoring committee will be organized for the purposes of data evaluation in this study.

The members of the committee will include [name], neurosurgeon in the Department of Neurosurgery who performs spinal surgeries yet is not involved in the implementation of this project, and [name], statistician in the Department of Epidemiology and Population Health who is not involved in this protocol. After 20 patients complete the study (approximately 10 patients in each arm), interim analyses will be performed to compare pain ratings, narcotic usage, time to ambulation, and time to discharge to control patients, and the data safety monitoring committee will be asked to review all results and advise the study personnel as well as the IRB about study continuation. If there a significant increase in any of these measured values beyond a single standard deviation of the mean, the data safety monitoring committee and the IRB will come to a decision regarding continuation of the study. Assuming the outcome follows a normal distribution, with 10 patients in each arm, and under the null hypothesis that there is no difference between two groups, the chance of observing a difference greater than or equal to one standard deviation between two groups is about 1/100000. With four measures considered here, the overall Type I error will be no greater than 5/100000. Therefore, the loss of power from the

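### For time to ambulation and time to discharge, the plan leaves the choice of final test, and of which outlying patients to drop, to judgement after the data are seen

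*Combined protocol and SAP*

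**What the plan says.** Section 2 (primary and secondary outcomes) lists time to first ambulation with physical therapy and length of stay among the primary outcomes.

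Section 7a sets the default: "Two sample T-tests will be performed to evaluate continuous variables", among them "time to first morphine dose, time to ambulation, and time to discharge". It then adds the switch: "Wilcoxon Rank Sum Test will be used if outliers are noted in the study population, detected as more than 5 MAD from the median", with a second condition attached, "and a concern presents that single patients may skew the data". The next sentence opens another route: "review of these patients who are outliers may also necessitate their exclusion from this work", if their data would materially move the mean of the remaining patients.

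Section 3 (sample size and power) words the switch differently and gives no threshold: "Ranked T-test may also be used if outliers are present". It also permits exclusion of patients with unusual post-operative courses when the prolonged stay is judged unrelated to pain control.

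The power analysis in section 7 sizes the trial on a mean difference. The only distributional information is one figure: "From our preliminary data, the standard deviation of time to discharge is 6.7 days". No mean, median or shape is given for time to discharge, and no SD for time to ambulation.

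**The concern.** The numeric threshold is written in advance, but the decision is not. Three things are left open.

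- **Whether the switch happens.** Section 7a requires a concern as well as a flagged value, without saying who judges it or by what criterion. Section 3 makes the rank test optional.
- **What counts as flagged.** The plan does not say whether the MAD is raw or scaled to the normal SD, or whether it is taken over both arms or within each.
- **Who stays in the analysis.** The same review of outliers can lead to exclusion instead of a rank test.

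Neither section says that the outlier review or the choice of test is made blind to allocation. The t-test and the rank test can reach different conclusions on the same data, so this freedom can decide whether a primary outcome is called significant, and the nominal 5% is no longer assured.

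**Working it through.** **1. The plan's own figures.** For two means, n per group = 2(z₁₋α/₂ + z₁₋β)²/d².
- d = 0.56, two-sided 0.05, 80% power: 2(1.960 + 0.842)²/0.56² = 50.06, so 51.
- d = 0.74, 95% power: 48, so 51 covers both.
- In days: 0.56 × 6.7 = 3.75 and 0.74 × 6.7 = 4.96, matching the stated 3.8 and 5.0.

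The sizing reproduces. It is a two-sided t-test calculation (one-sided would give 40).

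**2. How skewed is time to discharge likely to be?** Stay cannot be negative. A normal distribution with SD 6.7 puts a share Φ(−mean/6.7) below zero:

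| Assumed mean stay (days) | Share below zero | Skewness if log-normal | Skewness if gamma |
|---|---|---|---|
| 5 | 23% | 6.4 | 2.7 |
| 7 | 15% | 3.7 | 1.9 |
| 10 | 7% | 2.3 | 1.3 |
| 13.4 | 2% | 1.6 | 1.0 |

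(With c = 6.7/mean, skewness is c³ + 3c for the log-normal and 2c for the gamma.) Marked skew is likely if the mean is about 7 days or less. The phone call at 1 week and visit at 2 weeks in section 2 suggest a stay of that order but do not state it.

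**3. What the rule does to type I error.** Simulation under no treatment effect: 60 per arm, SD 6.7, stays rounded up to whole days, 5 MAD from the pooled median, 20,000 trials per case. Mean and shape are assumptions. Paired entries are raw / scaled MAD.

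| Stay, mean | Trials with a flagged value | Type I error: better of t and Wilcoxon once flagged | Same, with t-test after exclusion as a third choice |
|---|---|---|---|
| Log-normal, 7 | 99.7% / 94% | 7.0% / 6.9% | 9.2% / 8.7% |
| Log-normal, 10 | 98% / 78% | 6.7% / 6.3% | 8.3% / 7.7% |
| Gamma, 5 | >99% / 99% | 7.5% / 7.5% | 10.3% / 10.0% |
| Gamma, 7 | 98% / 75% | 6.8% / 6.4% | 8.6% / 7.5% |
| Gamma, 10 | 86% / 35% | 6.4% / 5.6% | 7.6% / 6.0% |

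Across all skewed cases run (log-normal means 5 to 15, gamma means 5 to 10), the ranges are 5.6–7.6% and 6.0–10.3%. A second run over means of 5 to 14 days gave 5.3–7.4% for the better of two tests.

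For comparison, the t-test alone gives 4.5–5.0%, Wilcoxon alone 4.7–5.1%, and the 5-MAD switch applied mechanically 4.7–5.1%. With normal data a value is flagged in 15% (raw) or 0.1% (scaled) of trials, so the undefined scale matters.

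**4. How often the choice matters.** With a true 30% reduction from a mean of 7 days, the two tests disagree on significance in 20% of log-normal and 17% of gamma trials. Power is 53% (t) against 64% (Wilcoxon) under the log-normal, and 51% (t) against 42% (Wilcoxon) under the gamma.

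**5. Can the planned 60 carry a fixed rank test?** For a 0.56 SD shift, Wilcoxon needs 50.06/0.955 = 52.4, so 53 per arm, if data are normal. At its worst-case efficiency for a shift it needs 50.06/0.864 = 57.9, so 58. Both fit within 60 if nobody is excluded.

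**The case against.** The strongest defence is that the plan does prespecify. It gives a numeric threshold, says Wilcoxon will be used beyond it, involves a statistician, and promises to explain any excluded patient in the write-up. If section 7a were followed as an automatic rule, type I error would stay near 5% (step 3). All of this stands. It does not answer the judgement clause, the optional wording in section 3 or the exclusion route, and explaining an exclusion afterwards does not restore the error rate.

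A reader might infer several stronger points, which the documents do not support:

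- **That the t-test is invalid for these stays.** At 60 per arm it held its level in every skewed case examined.
- **That the default costs power.** Under log-normal stays the automatic switch has almost the power of Wilcoxon (47.6% against 47.8% at mean 7, 25% shorter stay). Under gamma stays Wilcoxon loses to the t-test (31% against 37%). No document fixes the shape.
- **That the flag is nearly certain to fire.** It is for short, heavily skewed stays, but not for gamma stays with a mean of 10 days and a scaled MAD (35%).
- **That 6.7 days shows skew in both endpoints.** It describes time to discharge only, and even there the inference needs a mean that is not given.

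**Conclusion.** The concern holds as a matter of discretion, not of a wrong default test. For two primary outcomes, the plan lets the analyst settle the test and the analysis set after seeing the data, under two wordings that do not agree. Used to the full, that freedom raises type I error from 5% to about 5–7.5% when the choice is between the two tests once a value is flagged, and to about 6–10% when exclusion is a further choice. These are upper figures for an analyst who always takes the smallest p-value.

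They assume right-skewed stays, SD 6.7 days, mean 5 to 14 days and 60 per arm, and they shrink towards 5% as the mean lengthens and skew eases. They apply to time to discharge. For time to ambulation the gap in the plan is the same, but nothing in the documents allows its size to be calculated. This should be corrected because the remedy is cheap; it does not undermine the sample size.

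**What to change.** Name one primary test for each of the two endpoints now, applied to all randomised patients. One suitable choice is the Wilcoxon rank-sum test, with correction for ties if times are recorded in whole days. Report with it the Hodges-Lehmann estimate, described as the median of all pairwise between-arm differences and not as a difference in medians. Report the t-test mean difference as a prespecified sensitivity analysis. Fixing the t-test instead would remove the discretion over tests equally well; what matters is that one is fixed.

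Then:
- delete the judgement-based switch in section 7a and the optional ranked test in section 3;
- delete, for the primary analysis, the clauses in both sections that allow outlying or prolonged-stay patients to be excluded;
- give in-hospital deaths the worst rank, and reconcile this with the early-stopping text in section 7, which removes the data of a patient whose death is attributed to surgery.

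The cost is wording. With Wilcoxon as primary, the main estimate is no longer the mean difference in days on which section 7 sized the trial, and power may be somewhat higher or lower depending on the shape of the data.

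### If time to ambulation is recorded in whole days and MAD means median absolute deviation, the 5-MAD outlier screen breaks down once more than half the patients first walk on the same day

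*Combined protocol and SAP*

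**What the plan says.** Section 7a plans two-sample t-tests on outcomes it calls continuous, among them "time to first morphine dose, time to ambulation, and time to discharge". It then sets a numerical outlier criterion, "detected as more than 5 MAD from the median". MAD is not spelled out. The section does not say whether it is scaled, whether it is computed by arm or over both arms, or what happens if it is zero.

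Two consequences may follow a flag, each needing a further judgement:
- The Wilcoxon rank sum test replaces the t-test if outliers are found "and a concern presents that single patients may skew the data".
- Review of the flagged patients "may also necessitate their exclusion from this work if they provide data that will significantly modify the mean of the remaining patients".

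Under the heading on which data test the hypothesis, the same section lists "days until patients ambulate with physical therapy, pain ratings at 24 and 48 hours, and days to discharge", all from the medical record. The next item says the t-test on these data is subject to the outlier provisions just described, so the screen applies to the day-based outcomes. Section 2 lists time to first ambulation with PT as a primary outcome.

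**The concern.** A median absolute deviation measures spread well when values are finely graded. On a coarse scale with many ties it can be exactly zero while the data still vary. A threshold of five times zero is zero, so a patient one day from the median is treated like a patient three weeks from it.

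First ambulation after a one- or two-level lumbar fusion could plausibly fall on one day for most patients, although the documents do not say so. The screen would then stop separating aberrant values from ordinary ones. If the majority day is day 1, those flagged are almost all later walkers. If methadone speeds walking, more of them are controls. The patients opened to discretionary exclusion would be those who carry the treatment contrast on a primary outcome.

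**Working it through.** **Inputs.** From Section 7a: the threshold |x − median| > 5 × MAD, and ambulation in days. From the power analysis in Section 7: "We proposed to recruit 60 patients to undergo the new treatment and another 60 as controls", and an SD of 6.7 days for time to discharge. The share of patients walking on each day is not in the documents and is varied below as an assumption.

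**The plan's own figure.** No result is stated for the outlier rule. The nearest figure is the sample size, 51 per group for "power to detect an improvement of 0.56 (0.74) within-group standard deviation at statistical significance level 0.05". At 80% power and two-sided 0.05, n = 2(1.96 + 0.8416)² / 0.56² = 50.06, which rounds up to 51. This reproduces, and nothing below disturbs it.

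**Step 1: the threshold on whole days.** MAD = median of |x − median|. Take 120 patients pooled over arms, with those not on day 1 split equally between days 2 and 3:

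| On day 1 | Median | MAD | 5 × MAD | Flagged |
|---|---|---|---|---|
| 54 (45%) | 2 | 1 | 5 | 0 |
| 60 (50%) | 1.5 | 0.5 | 2.5 | 0 |
| 66 (55%) | 1 | 0 | 0 | 54 |
| 72 (60%) | 1 | 0 | 0 | 48 |
| 84 (70%) | 1 | 0 | 0 | 36 |

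The break is sharp. In one arm of 60, 30 patients on day 1 gives 0 flagged and 31 gives 29. The usual scaling does not help, because 5 × 1.4826 × 0 = 0.

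**Step 2: how often this would happen.** With day 1 as the commonest day, the pooled MAD is 0 when more than 60 of 120 walk on day 1. The day-1 count is the sum of two binomials, each with n = 60:

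| Day-1 share, control / methadone (assumed) | P(MAD = 0) |
|---|---|
| 35% / 50% | about 4% |
| 45% / 60% | about 68% |
| 55% / 70% | 99.7% (simulations gave 99.5% and 99.8%) |

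If the MAD is taken within one arm of 60, the chance that more than half share the day is 4%, 45% and 93% for true shares of 40%, 50% and 60%.

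**Step 3: who is flagged.** At 55%/70%, the expected flags are 60 × 0.45 = 27 controls and 60 × 0.30 = 18 methadone patients, 45 of 120 in all.

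**Step 4: what exclusion could do.** Assume days 1 to 4 in 55/27/12/6% of controls and 70/20/7/3% of methadone patients.
- Means: control 0.55 + 0.54 + 0.36 + 0.24 = 1.69; methadone 0.70 + 0.40 + 0.21 + 0.12 = 1.43; difference 0.26 days.
- If the flagged day 3–4 walkers were excluded: control (0.55 + 0.54)/0.82 = 1.33; methadone (0.70 + 0.40)/0.90 = 1.22; difference 0.11 days.

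This shows what the discretion allows. It does not predict how it would be used.

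**Step 5: time to discharge.** Lognormal stays with SD 6.7 and assumed means of 4 to 10 days, rounded up to whole days, put 9% to 27% of patients on the commonest day. In simulated arms of 60, P(MAD = 0) is at most 0.0001. A sample constructed with 31 of 60 on one day and a few very long stays has SD 6.9 and MAD 0. The stated SD therefore makes failure very unlikely but does not strictly exclude it.

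**The case against.** **The trigger is not in the documents.** This stands. No distribution of ambulation days is given, and the probability runs from about 4% to over 99% with the share assumed. A reader might infer that the screen will fail in this trial; the documents do not show that.

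**Whole-day recording is inferred.** This also stands. Section 7a calls the times continuous, Section 2 says time-to-event data will be in the chart, and the power analysis uses days with decimals. On clock times the problem should largely disappear. Against this, the only description of the ambulation data used to test the hypothesis is in days.

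**MAD might mean mean absolute deviation.** It would then not be zero in these examples, and 0 to 3 of 60 would be flagged. The undefined term is itself a gap.

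**It covers one outcome at most.** A reader might extend the failure to every outcome counted in days. Step 5 does not support that for discharge.

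**A flag does nothing alone.** Correct. A reader might infer that some 45 patients would be dropped, but exclusion is discretionary and tied to an effect on the mean. Under the Step 4 control distribution, removing one day-2 walker moves the arm mean by (2 − 1.69)/59 = 0.005 days, and one day-4 walker by (4 − 1.69)/59 = 0.04 days. Judged singly, such patients hardly meet the condition. A switch to a rank test would do little harm, and the plan promises a written account of outliers. But the condition has no numerical limit and does not say that patients are to be judged singly.

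**The discretion is the larger problem.** Discretionary exclusion and test switching would remain a weakness under any threshold. That does not make a detector that can fail on a primary outcome acceptable.

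**Conclusion.** The point holds conditionally, for time to ambulation only. It rests on three assumptions: values in whole days, MAD as median absolute deviation, and more than half the patients first walking on the same day. When all three hold, the flagged number among 120 goes from none at 50% on day 1 to 54 at 55%, and the screen carries no information about aberrant values. How likely this is cannot be settled from the documents.

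No effect on type I error or power has been shown, and the sample size is untouched. The point still merits correction because the flag is the only numerical criterion before patients may be excluded from a primary outcome, and when day 1 is the majority day those exposed are almost all later walkers, more of them controls if methadone works.

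**What to change.** In Section 7a, for time to ambulation:
- Do not apply the 5-MAD screen to whole-day counts. Check implausible values against the chart and correct recording errors.
- If a screen is kept, compute it on elapsed hours taken from the chart. Define MAD as the scaled median absolute deviation, and state that the screen does not apply when the MAD is 0.
- State that no patient is excluded from the ambulation analysis because of this flag.

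The cost is wording only, plus abstraction of clock times if the hours option is chosen. Sample size, visits and treatment do not change.

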Age <21 or >80, renal failure requiring dialysis or serum creatinine greater than 2.0, significant hepatic dysfunction (liver function tests greater than twice the upper limit), hepatic cirrhosis, pulmonary disease requiring home oxygen therapy, obstructive sleep apnea, severe heart disease, allergy to methadone, morphine, ketamine or fentanyl, **recent or distant history of opioid abuse,** opioid use equal to or greater that the equivalent of 10mg morphine per day, poorly managed psychiatric illness, a known history of alcohol abuse, morbid **obesity (for the purposes of this study body mass index > 50 kg/m2),** treatment with other NMDA receptor antagonists, HIV-1 protease inhibitors, erythromycin or ketoconazole, prolonged QTc on pre-operative EKG, and the refusal or inability to sign the consent form to agree to participate in this study.

State primary and secondary outcome(s)

The primary outcomes for the study include total narcotic dose post-operative, frequency of narcotic use, the time to first ambulation after surgery with PT, length of stay, disposition (i.e. level of rehabilitative care), and improvement on clinical questionnaires in the intervention group as compared to the control group. Secondary outcomes include better subjective pain control, need for post-operative course of

dexamethasone for post-operative/post-fusion radiculopathy or neurapraxia/neuropathy and fusion at 3-6 months.

> For Randomized clinical trials

• Indicate whether a parallel or crossover study, and the number of treatment groups
The study will take the form of a parallel, 2 arm analysis of a methadone treatment group or a
group receiving the current standard of care without intra-operative methadone administration.

• Describe randomization and blinding procedures

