• For studies with complicated schedules, provide a 1-page table or flow diagram.

N/a

• State the plan for obtaining HIPAA authorization (or waiver as appropriate).

HIPAA authorization and wording will be included in the consent form and will completed during the consent process prior to surgery.

6) Risk/Benefit

• Identify all anticipated risks (e.g. medical, social, psychological, and/or legal).

Medical risks of methadone include the risks of using any opioid narcotic, which include overdose leading to respiratory depression, dependence and QTc prolongation. Psychological risks include obtunded, lethargic state or altered mental status due to long half-life and opioid effects post-operatively and any resultant mental distress, especially in opioid-naïve patients

• Describe how anticipated risks will be minimized.

The risk of overdose will be minimized as the trained anesthesiologist during the procedure will carefully calculate dose according to their protocol as specified, normally carried out for their routinely administered opioids, and will have naloxone readily available should a patient show signs of overdose. Patient will be closely monitored by nursing staff post-extubation for signs of respiratory depression, as with any other post-operative patient who received intra-op opioids.

The risk of opioid dependence – highly unlikely given one dose of the drug

The risk QTc prolongation has been proven to be negligible except in chronic methadone use, nevertheless – patients with prolonged QT intervals are at increased risk for Torsades de pointes and excluded from this study when identified on pre-operative testing.

The psychological risks will be minimized by warning patients of the possibility of mental lethargy post operatively during initial recruitment and consent. However, given that these risks are shared with other anesthetic agents being used during the procedure and the quality and degree of post-operative monitoring, it is likely that this risk is minimal when compared to non-study patients undergoing the same procedure.

- Document how potential benefits to participants or others justify potential risks.

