interim analysis is negligible. If the methadone intervention contributes greater than normal adverse events (>2 patients) the study will be held from further recruitment. The study medication will not be administered further, no dosing changes will be made, and the IRB will be informed. A decision at this point will be reached regarding further accrual. If a patient should die prior to discharge, a thorough cause analysis will be implemented by the DSMB, the IRB, in addition to the analysis that will already be performed by the hospital. If it is due to the surgery outside of the trial mediation, the data for this patient will not be used and the information will be explicitly reported in any publication yet kept separated from the other patient's data, as it would not be feasible or make sense to include this patient in the analysis. If this adverse event is found to be caused by the methadone administration, the trial will be stopped. This is however an extremely unlikely scenario as methadone is used daily by millions of individuals, has already been approved by the FDA, and our study patients will undergo a rigorous screening, namely for QTc prolongation, to remove any potential risk of death as a result of methadone administration. The only wayy to address this possibility is to have a plan to remove this patient's data from the other patient's data, with a clear note made in the report.

Describe how possible confounding and/or effect modification will be addressed. The possible confounders have been addressed via the strict inclusion and exclusion criteria of the study. Other confounding variables including past narcotic usage, and a cutoff of <10mg equivalents of morphine will be considered when selecting patients for participation in this study. Such a low daily morphine dose is unlikely to significantly impact methadone effect or post-operative narcotic use in patients with this low level of narcotic usage compared to narcotic-naïve patients. Patient time to ambulation will be confounded by baseline neurological status and therefore we will randomly assigning patients to each arm of the study as described above. Confounding in regards to time of operative procedure and complexity of surgery will be controlled properly with appropriate randomization.

Describe how loss to follow up will be addressed

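### Randomised patients can be removed after their outcomes are known, and no analysis of all randomised patients is planned

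*Combined protocol and SAP*

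**What the plan says.** Three provisions take randomised patients out of the comparison.

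- **Outliers** (section 7, Data Analysis, part a). Values more than 5 MAD from the median first lead to a Wilcoxon test. In addition, review of these patients "may also necessitate their exclusion from this work if they provide data that will significantly modify the mean of the remaining patients". No threshold is given for a significant change in the mean. The plan does not say whether the MAD is scaled, or whether it is taken over both arms or within each.
- **Long stays** (section 3, Study Population, sample size item): "patients with unusual post-operative courses may be excluded if their reason for prolonged hospitalization is unrelated to immediate post-operative pain" control. This is also discretionary.
- **Deaths before discharge** (section 7, interim analysis item), after a cause review: "If it is due to the surgery outside of the trial mediation, the data for this patient will not be used". This one is a fixed rule. The same item closes with a general intention to separate a deceased patient's data, so the handling of a death attributed to methadone is unclear.

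The sample size is meant to absorb removals: "The large sample size plans to take into account possible outliers that may not be included in final analysis". The nearest the plan comes to an analysis population is "a sample of 60 completed methadone patients will be evaluated against 60 randomized, standard narcotic regimen controls". The primary outcomes in section 2 include total post-operative narcotic dose and "the time to first ambulation after surgery with PT, length of stay".

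**The concern.** Randomisation makes the two arms comparable only while everyone randomised is counted. The outlier rule selects on influence over the result. The long-stay rule selects on a primary outcome, and on a judgement about its cause.

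The long-stay rule is the most direct problem. Section 6 lists respiratory depression among the risks of methadone, and also "obtunded, lethargic state or altered mental status due to long half-life and opioid effects post-operatively". A stay prolonged by one of these can be read as having no pain-control reason, so the patient may be dropped from the very comparison that should register the effect.

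Section 2 blinds the staff who collect outcomes. It does not say who decides on exclusions or whether they know the arm. The removed patients would be described in the write-up, so the events would not disappear. The estimated difference in stay would still be wrong.

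**Working it through.** **1. The plan's own figure.** Inputs from section 7 (power analysis): difference 0.56 SD, 80% power, "at statistical significance level 0.05 as had been calculated to be 51 patients per group". Two-sided normal approximation: n = 2(1.960 + 0.842)²/0.56² = 50.1, rounded up to 51 per group (the t-test gives 51.03). The figure reproduces. In days, 0.56 × 6.7 = 3.75, matching the stated 3.8. The sample size is sound; the defect is the analysis population.

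**2. Long-stay rule, by arithmetic.** If k of 60 methadone patients stay D extra days for a non-pain reason, the true difference in mean stay is kD/60. Assumed: k = 3 to 6 and D = 7 to 14.

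- Smallest case: 3 × 7/60 = +0.35 days. Largest case: 6 × 14/60 = +1.40 days.
- If all affected patients are dropped, about 0 remains.
- If three of the six are dropped at 14 days, 3 × 14/57 = +0.74 remains.

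This needs no assumption about the shape of the stay distribution. Against the 3.8-day detectable difference, 0.35 to 1.40 days is 9% to 37%.

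**3. The 5-MAD rule, by simulation.** Inputs: SD 6.7 days (section 7), 60 per arm, pooled median and MAD. Assumed: lognormal stay with mean 4 to 10 days, since the plan gives no mean, and automatic removal of every flagged value. The true harm is 14 extra days in 5% of methadone patients (0.05 × 14 = +0.7 days) or 10% (+1.4 days). Each cell shows raw MAD / MAD scaled by 1.4826.

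| Assumed mean stay (days) | Flagged, no effect (%) | Left of +0.7 days | Left of +1.4 days |
|---|---|---|---|
| 4 | 10.3 / 6.2 | 0.00 / 0.05 | 0.00 / 0.18 |
| 6 | 7.2 / 3.6 | 0.13 / 0.44 | 0.35 / 0.97 |
| 8 | 5.2 / 2.2 | 0.31 / 0.54 | 0.73 / 1.14 |
| 10 | 3.9 / 1.3 | 0.40 / 0.60 | 0.89 / 1.23 |

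The flagged share is about 2 to 12 of 120 patients. If stay were normal, 5 raw MAD would be 5 × 0.6745 = 3.37 SD, only 0.075% would be flagged, and the rule would hardly matter.

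Removal can also work against the trial's own hypothesis. A true 2.0-day reduction, modelled as a proportional shortening of stay, is estimated as 0.97 to 1.66 days after even-handed removal (means 6 to 10).

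**4. Type I error with no true effect (same model).**

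- Removal from both arms by a fixed rule: 4.7-5.1%.
- The written switch from t-test to Wilcoxon: 4.8-5.0%.
- Free choice of the best of three tests (t-test on everyone, t-test without outliers, Wilcoxon): 8.0-9.9%.
- Removal from the methadone arm only: a spurious reduction of 0.4 to 1.6 days.

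The last two are upper bounds. The plan does not prescribe them, but nothing in it rules them out.

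**5. Power if everyone is kept.** At 0.56 SD the two-sided t-test has 80.0% power with 51 per arm and 86.0% with 60. With 60 per arm, the difference detectable with 80% power is 0.516 SD, so 3.8 days stays detectable while the all-patient SD is at most 3.8/0.516 = 7.4 days.

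**The case against.** The strongest reply is that the harm is conjectural and the plan has safeguards.

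- **Reading of the long-stay rule.** The drugs that cause over-sedation are the pain control, so an opioid complication could count as related to pain control and be kept. That reading is open, and the bias is therefore possible, not certain. The wording does not settle the matter.
- **The hold on recruitment.** Section 7 holds recruitment if methadone contributes to excess adverse events in more than two patients, so three to six affected patients might trigger it. With two patients the shift is 2 × 7/60 = 0.23 to 2 × 14/60 = 0.47 days, or 6% to 12% of 3.8 days. This may limit the size. It does not reach long stays that nobody attributes to methadone, and it returns no patient to the analysis.
- **The assumed extra days.** Nothing in the documents supports 7 to 14 extra days after a single dose, and the background reports no excess of adverse events. This is fair; the figures are illustrations.
- **Automatic removal.** The table removes every flagged value, whereas section 7a goes to Wilcoxon first and excludes only after review. The table therefore shows the full-removal case, and its results vary widely with the assumed mean.
- **Retention and disclosure.** In-hospital data of patients lost to follow-up may be kept if complete to discharge, no drop-out is expected, excluded patients will be explained in the write-up, and deaths go to the monitoring board and the IRB. All true, but none of it provides an analysis that includes the removed patients.
- **Scope.** Only length of stay is quantified here. No effect on pain scores or narcotic dose has been shown.

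**Conclusion.** The concern holds and should be corrected before any data are examined by arm. All three removal routes are in the text, the plan gives no all-randomised analysis, and it does not require blinded exclusion decisions. That much rests on the wording alone.

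The size is conditional. Under the assumed long-stay scenarios, a true excess of 0.35 to 1.40 days can be reduced to about zero. Under lognormal stay with full removal of flagged values, the 5-MAD rule leaves between 0 and 1.23 days of a true 1.4-day excess, depending mainly on the mean stay and the MAD scaling, neither of which is given. With no treatment effect and even-handed use, that rule does not inflate type I error, and with normal stay it would hardly operate.

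**What to change.** 1. Define the primary analysis as all randomised patients in their assigned arms, and take the exclusion provisions in sections 3 and 7 out of it.
2. Fix the test for each outcome before any data are seen by arm. Where outliers are expected, use the Wilcoxon test that section 7a already names, and report mean differences alongside.
3. State in advance how a death before discharge counts for each outcome, whatever its cause. One option is worst rank for time to discharge and time to ambulation. Narcotic dose needs its own rule, because an early death lowers the total.
4. Keep exclusions only as a labelled sensitivity analysis, with written criteria (including the MAD scaling and reference group) applied by people blind to arm.

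The cost is wording only. The 60 − 51 = 9 patients per arm above the calculated size then add power (86% instead of 80% at 0.56 SD) and are not spent on exclusions. If the 6.7-day SD left out long-stay patients, 80% power for 3.8 days still holds up to an SD of about 7.4 days.
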